### 3.1.5 Prior and Concomitant Medications

Medications taken by any participant at any time during the study will be coded using the anatomical therapeutic classification (ATC) system within the World Health Organization (WHO) Drug Dictionary.

Medications will be categorised for analysis according to their onset and end dates as follows:

- Prior medications:
  - end date  $\leq$  date of first dose of IP
- Concomitant medications during on-treatment period:
  - end date  $>$  date of first dose of IP and start date  $\leq$  earliest (date of last dose of IP + 33 days, date of death, date of study withdrawal), or
  - end date ongoing and start date  $\leq$  earliest (date of last dose of IP + 33 days, date of death, date of study withdrawal)
- Concomitant medications during post-treatment period (for participants still being followed up then):
  - start date  $>$  date of last dose of IP + 33 days.

The handling of partial/missing dates for prior/concomitant medications is detailed in Appendix 8.3.

Essentially the above says that:

- Prior and concomitant medications are mutually exclusive.
- Concomitant medications on-treatment and post-treatment are also mutually exclusive (here, the word “concomitant” means concomitant with study procedures, irrespective of whether IP was still being taken). Specifically, a concomitant medication which started on-treatment and ended post-treatment will only be considered on-treatment.

If the medication record has a completely missing onset date, the participant will be assumed to have been on the medication on the date of the first study procedure. If the medication record has a partially missing onset date (month/year or year only) which is the same as that for the end of IP treatment, it will be assumed to have started on-treatment. If the medication record has a partially missing onset date (month/year or year only) which is the same as that for the start of IP treatment, it will be assumed to have started before treatment.

If the medication record has a completely missing end date, the participant will be assumed to have been on the medication on the date of study completion or withdrawal. If the medication record has a partially missing end date (month/year or year only) which is the same as that for start of IP treatment, it will be assumed to have ended on-treatment. If the medication record has a partially missing end date (month/year or year only) which is the same as that for end of IP treatment, it will be assumed to have ended post-treatment.

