### 3.6.2 General Adverse Events

Adverse events experienced by any participant at any time during the entire study will be coded using Medical Dictionary for Regulatory Activities (MedDRA V27.0). AEs will be categorised for analysis according to their onset date into the following study periods:

- AEs occurring during screening/run-in period: date of Visit 1 ≤ AE onset date < date of first dose of IP
- AEs occurring during on-treatment period: date of first dose of IP ≤ AE onset date ≤ earliest (date of last dose of IP + 33 days, date of death, date of study withdrawal)
- AEs occurring during post-treatment period: date of last dose of IP + 33 days < AE onset date ≤ study completion or withdrawal date
- AEs occurring during on-study period: date of first dose of IP ≤ AE onset date ≤ study completion or withdrawal date.
- AEs occurring during the additional FU period: date of Visit 19 ≤ AE onset date ≤ study completion or withdrawal date.

If the AE has a completely missing (and unresolvable) onset date, then the AE will be assumed to have occurred during the on-treatment period, unless the end date indicates unambiguously that the AE resolved before treatment started. If the AE has a partially missing (and unresolvable) onset date, then the AE will also be assumed to have occurred during the on-treatment period, unless either the end date indicates unambiguously that the AE resolved before treatment started, or the partial onset date is in the month/year prior to start of treatment.

The handling of partial/missing dates for AEs is detailed in [Appendix 8.3](#).

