### 8.3 Partial dates for adverse events and prior/concomitant medications

Dates missing the day, or both the day and month of the year adhere to the following conventions to classify AEs and to classify prior/concomitant medications:

- The missing start day is set to:
  - First day of the month of occurrence, if the start YYYY-MM is after the YYYY-MM of first study treatment
  - The day of the first study treatment, if the start YYYY-MM is the same as YYYY-MM of the first study treatment
  - The date of informed consent, if the onset YYYY-MM is before the YYYY-MM of the first study treatment.
- The missing end day is set to:
  - The last day of the month of the occurrence, if the end YYYY-MM is after the YYYY-MM of the first study treatment.
  - Death date if the participant died in the same month.
  - The day of last study treatment if the YYYY-MM of occurrence is the same as the last study treatment.
- If the start date is missing both the day and month, the start date is set to:
  - January 1 of the year of occurrence.
  - The date of the first study treatment, if the start year is the same as the year of the first study treatment
- If the end date is missing both the day and month, the date is set to:
  - December 31 of the year of occurrence.
  - Date of death if the participant died in the same year.
  - Last study treatment date if the year of occurrence is the same as the last study treatment date.

- If the start date is null, the date is set to:
  - The date of first study treatment.
  - January 1 of the same year as the end date, if the end date suggests that the start date could be prior to the date of first study treatment.
- If the end date is null and not recorded as ongoing, the date is set to:
  - The date of the first study treatment, if the start date is prior to the date of first study treatment.
  - The date of last visit, if the start date is on or after the date of first study treatment.
- If the end date is null and recorded as ongoing, the end date is not imputed.

Signature Page for VV-RIM-02702313 System v5.0

D5242C00001 SAP Edition 4

Approve: Document Level Task  
Verdict: Approved

PPD

Content Approval

21-Aug-2024 20:36:52 GMT+0000

Approve: Document Level Task  
Verdict: Approved

PPD

Content Approval

21-Aug-2024 20:42:05 GMT+0000

Signature Page for VV-RIM-02702313 System v5.0

D5242C00001 SAP Edition 4

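### SAP 3.1.5 and 3.6.2 conflict with Appendix 8.3 for two kinds of missing date, and the SAP does not say which rule governs

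*SAP*

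**What the plan says.** **Medications.** SAP 3.1.5 classifies by end date: on or before first dose is prior, later or ongoing is concomitant. It adds that "Prior and concomitant medications are mutually exclusive". For a missing end date its rule begins "If the medication record has a completely missing end date, the participant will be assumed to have been on the medication on the date"; the date meant is when the participant completes or withdraws. Appendix 8.3 covers an end date that is null and not recorded as ongoing. If the drug started before first dose, the end date becomes "The date of the first study treatment, if the start date is prior to the date of first study treatment"; if it started on or after first dose, it becomes the last visit.

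**Adverse events.** SAP 3.6.2 says that if the onset date is partly missing, "then the AE will also be assumed to have occurred during the on-treatment period". There are two exceptions, and both concern events before treatment. Appendix 8.3 instead imputes a date. For a missing day it is "First day of the month of occurrence, if the start YYYY-MM is after the YYYY-MM of first study treatment"; for a year-only onset after the first-dose year it is 1 January of that year. Section 3.6.2 defines post-treatment as onset later than last dose + 33 days.

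**Cross-references.** Both 3.1.5 and 3.6.2 refer to Appendix 8.3 for the handling of partial and missing dates, yet each also states its own rules. No sentence ranks one above the other.

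**The concern.** Two programmers could each follow the SAP and put the same record in different categories. For medications, the prior and concomitant tables in SAP 4.2.4 would differ. So could the table of disallowed concomitant medications, whose entries the SAP treats as important protocol deviations: under Appendix 8.3, a prohibited drug begun before first dose with a blank, not-ongoing end date would leave it. For adverse events, the on-treatment counts and exposure-adjusted incidence rates (EAIR) in SAP 4.2.10.1 would differ.

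In each case one of the stated rules also gives a poor answer. Appendix 8.3 stops a drug of unknown end date on the day treatment begins, which removes it from the concomitant tables. Section 3.6.2 counts as on-treatment an event whose recorded month or year shows that it began after the on-treatment window closed.

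**Working it through.** The plan gives no figure to reproduce, so the check applies each rule to the same hypothetical record. The assumed dates, which are not from the documents, are: first dose 15 March 2022, last dose 14 February 2023, study completion 6 June 2023. The on-treatment period (SAP 3.1.3) ends at last dose + 33 days: 14 February 2023 + 33 = 19 March 2023.

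**Medication, started 1 November 2021, end date null, not ongoing**
- 3.1.5: end = 6 June 2023, later than 15 March 2022. The start is before 19 March 2023, so the drug is concomitant on-treatment.
- 8.3: end = 15 March 2022, which is on or before first dose, so the drug is prior.
- Result: conflict.

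**Adverse event, onset month known, day missing**

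| Recorded onset | 3.6.2 | 8.3 date | 8.3 period |
|---|---|---|---|
| Jan–Feb 2022 | before treatment | consent date | before treatment |
| Mar 2022 | on-treatment | 15 Mar 2022 | on-treatment |
| Apr 2022–Mar 2023 | on-treatment | 1st of month | on-treatment |
| Apr, May, Jun 2023 | on-treatment | 1st of month | post-treatment |

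Only the last row conflicts.

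**Adverse event, onset year only, 2023.** Take a participant with last dose 1 November 2022. The window ends 1 November + 33 days = 4 December 2022. Section 3.6.2 gives on-treatment; 8.3 gives 1 January 2023, which is post-treatment. This also conflicts.

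**Medication patterns where the imputed date differs but the category does not**
- Start day missing in the first-dose month: 3.1.5 says of an onset "which is the same as that for the start of IP treatment, it will be assumed to have started before treatment", while 8.3 uses the first-dose day. With a null end date, both routes give concomitant.
- End day missing in the last-dose month: 3.1.5 says of an end date "which is the same as that for end of IP treatment, it will be assumed to have ended post-treatment", while 8.3 uses "The day of last study treatment if the YYYY-MM of occurrence is the same as the last study treatment". For a drug started during treatment, both give concomitant on-treatment.
- Start on or after first dose with a null end date, and start and end both null: both give concomitant.

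**A gap in 8.3.** When only the end day is missing and the end month is the first-dose month, 8.3 has no rule unless that month also contains the last dose or death. Section 3.1.5 covers the case: ended on-treatment.

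**Why 8.3 is the better base for adverse events.** Its onset dates in the table's later rows are the earliest compatible with what is recorded, so an event becomes post-treatment only when the known part of the date rules out on-treatment. Section 3.6.2 assigns a period but no date, and the EAIR needs time to first event.

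**The case against.** The strongest reply is that the intended precedence can be seen. Both sections send the reader to Appendix 8.3 for the detail, and the SAP amendment history records that 8.3 was added for 3.1.5 and 3.6.2. On that view the older paragraphs are leftover text. That is a fair reading of intent, and it supports using 8.3 as the base. It does not settle the matter: the older paragraphs are still operative sentences, no precedence is written, and 8.3 taken unchanged would keep the doubtful null-end-date rule and the first-dose-month gap.

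It is also fair that the deviation need not be lost with the table entry. SAP 2.2 has the study team identify important deviations before unblinding, with separate categories for excluded medications and eligibility.

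A reader might infer more than the documents support:
- **That every prohibited drug without an end date disappears.** It does not. A drug started on or after first dose is carried to the last visit under 8.3, and one marked ongoing has no end date imputed and stays concomitant.
- **That the different start dates for the first-dose month flip the category.** They do not, because prior versus concomitant depends on the end date.
- **That a partial start date for systemic corticosteroids becomes a Day 1 event in H02d or H04, or an immediate intercurrent event for the co-primaries.** Appendix 8.3 is limited to classifying adverse events and prior or concomitant medications, and 3.1.5 has the same purpose for medications. The time-to-event derivations (SAP 3.3.3) and the intercurrent-event handling (SAP 4.2.6.1) do not invoke either.

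**Conclusion.** The contradiction is real for two record types: a drug started before first dose with a null, not-ongoing end date, and an adverse event whose known onset month or year lies wholly after last dose + 33 days. The first moves between concomitant and prior, the second between on-treatment and post-treatment.

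This is a minor point of drafting. It touches medication tables and on-treatment AE and EAIR tables. On-study AE counts do not move, and no confirmatory endpoint, alpha level or model is involved. The documents do not give the number of affected records, so the effect on any table cannot be sized. The conclusion rests on the SAP wording; the calendar dates above only illustrate it.

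**What to change.** Make Appendix 8.3 the single rule set, and delete the imputation paragraphs in SAP 3.1.5 and 3.6.2, leaving the cross-references. In 8.3:

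1. Change the rule for a null end date not recorded as ongoing, so that a drug started before first dose is carried to the last visit. This gives the same category as 3.1.5.
2. Add the 3.1.5 rule for a partial end date in the first-dose month (ended on-treatment), which 8.3 lacks at day level.
3. Leave the adverse-event onset rules as they are.

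The cost is SAP text only. A few more drugs would count as concomitant than under the present 8.3, and a few adverse events would move from on-treatment to post-treatment relative to 3.6.2.

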### Background INCS/MFNS

The background INCS medications should be maintained at a stable dose from Visit 1 and throughout the screening and study period and no other medications intended to prevent polyp recurrence should be used. All participants will use INCS for a minimum of 4 weeks prior to V3 and continued throughout the study period.

Standardized MFNS (50 µg/actuation) nasal spray is contained in a bottle with 120 actuations for US and 140 actuations for all other countries. Two doses of MFNS (50µg/actuation) in each nostril twice daily (total 400µg daily) or equivalent INCS will be administered unless there is a medical rationale to use the lower dose (QD) regimen.

#### **3.1.6 Subgroups**

The following subgroups are defined for the purposes of efficacy subgroup analysis.

- Age category at screening visit (<65,  $\geq$ 65 years)
- Gender at screening visit (male, female)
- Race at screening visit (white, non-white)
- Prior surgery for NP status (yes, no)
- Allergic rhinitis at screening visit (yes, no)
- Co-morbid asthma/AERD/NSAID-ERD status at screening visit (yes, no)
- AERD/NSAID-ERD at screening visit (yes, no)
- Baseline eosinophil count (<150,  $\geq$ 150 to <300,  $\geq$ 300 eosinophils/ $\mu$ L)
- Baseline BMI (< 30 kg/m^2,  $\geq$  30 kg/m^2)
- Region (China, Japan, ROW)
- Region (Asia Pacific including China and Japan, Europe, North America)
- Baseline NPS (<median,  $\geq$  median)
- Baseline NCS (< median,  $\geq$  median)
- Time since last NP surgery at screening visit (<3 years,  $\geq$ 3 years)
- Number of previous NP surgeries (0, 1, 2 or more)
- Prior SCS use for NP (yes, no)

- Baseline weight quartiles
- Baseline staphylococcus aureus colonization in nasal culture (yes, no, not applicable)
- Baseline eosinophil count quartiles
- Baseline total serum IgE quartiles
- Baseline perennial specific IgE status:
  - Any perennial FEIA positive: requires 1 or more specific IgE (FEIA) panels to be positive. Provided that at least one IgE panel is positive, no further requirement is made for data on all 7 panels for all countries, excluding China, and all 6 panels for China only to be available.
  - All perennial FEIA negative: requires all 7 specific IgE panels to be negative for all countries, excluding China, and all 6 specific IgE panels to be negative for China.
  - If there are fewer than 7 panels for all countries, excluding China and less than 6 panels for China with data available and none of these is positive, then IgE status is considered “Unknown perennial FEIA”.
  - Positive is defined as a value  $\geq 0.35$  kU/L.
  - The 7 panels for all countries, excluding China include: IgE American Cockroach, IgE Cat Dander, IgE D. farina, IgE D. pteronyssinus, IgE Dog Dander, IgE German Cockroach, and IgE Mould Mix 1..
  - The 6 panels for China only include: IgE Dog Dander, IgE Cat Dander, IgE D. farinae, D. pteronyssinus, IgE German Cockroach, and IgE Mould Mix 1.
- Baseline seasonal specific IgE status:
  - Any seasonal FEIA positive: requires 1 or more specific IgE (FEIA) panels to be positive. Provided that at least one IgE panel is positive, no further requirement is made for data on all 4 panels for all countries, excluding China and all 4 panels for China only to be available.
  - All seasonal FEIA negative: requires all 4 specific IgE panels for all countries, excluding China and all 4 specific IgE panels for China only to be negative.
  - If there are fewer than 4 panels for all countries, excluding China and China only with data available and none of these is positive, then IgE status is considered “Unknown seasonal FEIA”.
  - Positive is defined as a value  $\geq 0.35$  kU/L.
  - The 4 panels for all countries, excluding China include: IgE Grass Mix Pollen, IgE Silver Birch Pollen, IgE Weed Mix Pollen, and IgE Japanese Cedar.
  - The 4 panels for China only include: IgE Common Ragweed, IgE Common Silver Birch, IgE Mugwort, and IgE Goosefoot.

### 3.1.7 Other Baseline Characteristics

In addition to the subgroups in Section 3.1.6, the following baseline characteristics will be provided:

- Weight
- Height
- Baseline NPS, NCS, loss of smell, SNOT-22, LMK, and NPSD TSS
- Baseline lung function (FEV1, FEF 25-75%, FVC), ACQ-6, and FeNO for the asthma/AERD/NSAID-ERD subset
- Baseline NPIF
- Baseline eosinophils and IgE
- JESREC scores (<11,  $\geq$ 11) including participants from China only ([Tokunaga et al., 2015](#))

### 3.1.8 Disposition

The following definitions will be used for time to event variables in Kaplan-Meier disposition plots:

#### Time to last dose of IP

Time to last dose of IP will be defined as follows:

$$\text{Time to last dose (days)} = [\text{Date of last dose of IP from eCRF} - \text{date of first dose of IP}] + 1.$$

Date of last dose of IP will be the date of last dose taken from the “Discontinuation of Investigational Product” electronic case report form (eCRF) page for all participants, including those who prematurely discontinue IP as well as those who complete IP dosing as per protocol.

#### Time to premature study withdrawal

Time to premature study withdrawal will be defined as follows:

$$\text{Time to premature study withdrawal (days)} = [\text{study withdrawal date from eCRF} - \text{date of randomisation}] + 1.$$

Study withdrawal date will be the completion or discontinuation date from the “Disposition” eCRF page, where any participant status other than “Completed” has been entered.

Participants who did not prematurely withdraw from study will be censored at one of the following dates:

- Completion or discontinuation date from the “Disposition” eCRF page, where participant status of “Completed” has been entered.
- At primary database lock (DBL), ongoing participants will be censored at data cut-off date.

## 3.2 Primary Efficacy Variables

### 3.2.1 Change from baseline in total nasal polyp score at Week 52

The total NPS will be used to evaluate participant’s NP size throughout the study by the nasal endoscopy. The total NPS and the changes from baseline at Week 52 will be calculated for the co-primary efficacy endpoint.

The total NPS is the sum of the right and left nostril scores (maximum of 8), as evaluated by nasal endoscopy. The left and right score will be based on a central read with a scale from 0 to 4 as listed in [Table 4](#). Each nasal endoscopy is evaluated by two independent physician reviewers. The process of evaluation differs between confirmation of eligibility criteria and collection of scores for efficacy analysis. As a consequence, the NPS scores are derived differently for eligibility and efficacy use.

NPS score derivation to confirm eligibility criteria at Visit 2: If polyp scores for left and right nostril (maximum of 4 per each nostril) provided by two reviewers are:

- exactly the same, then the NPS score is the sum of right and left nostril scores provided by one reviewer,
- different for right and/or left nostril but the sum for each reviewer is  $>5$ , then the NPS score is calculated as the mean of right and left nostril scores provided by both reviewers,
- different for right and/or left nostril and the sum for one reviewer is  $<5$ , then the nasal endoscopy is evaluated by an independent adjudicator. The NPS score is the sum of left and right nostril scores provided by the reviewer selected by adjudicator.

NPS score derivation for efficacy analysis use: If polyp scores for left and right nostril provided by two reviewers at the same visit are:

- exactly the same, then the NPS score is the sum of right and left nostril scores provided by one reviewer at this visit,
- different for right and/or left nostril, then the nasal endoscopy is evaluated by an independent adjudicator. The NPS score at this visit is calculated as the sum of scores for left and/or right nostril selected by adjudicator, ie. there is no requirement the right and left nostril scores selected by adjudicator are provided by the same reviewer.

**Table 4 Endoscopic Nasal Polyp Score Within a Nostril**

Polyp score	Polyp size
0	No polyps
1	Small polyps in the middle meatus not reaching below the inferior border of the middle turbinate
2	Polyps reaching below the lower border of the middle turbinate
3	Polyps reaching the lower border of the inferior turbinate or a middle meatal polyp with a score of 2 with any additional polyp medial to the middle turbinate
4	Large polyps causing complete or near-complete obstruction of the inferior nasal cavity i.e. touching the floor of the nose

### **3.2.2 Change from baseline in nasal congestion score at Week 52**

Participant reported nasal congestion (NC) will be evaluated as part of the NPSD. The NCS (nasal congestion score) is captured by one item in the NPSD asking participants to rate the severity of their worst NC over the past 24 hours using the following response options: 0 – None; 1 – Mild; 2 – Moderate; 3 – Severe. Baseline will be the mean of daily responses from Day -13 to Day 0. Bi-weekly (14-day) mean NCS will be calculated if at least 8 days in each 14-day period has evaluable data; otherwise the bi-weekly mean is set to missing. The NCS and the changes from baseline at Week 52 will be calculated for the co-primary efficacy endpoint.

Additional, based on the Meaningful Change Thresholds (MCT) reported in Shih et al., 2023, participants with change from baseline in bi-weekly mean NCS  $\leq$  -1.0 will be defined as NCS responders.

